Official Title: Phase II - Safety-Enhancing Motor Vehicle Child Safety
Seat

NCT Number: NCT06384989

Document Date: May 2024

Document Contents: Study Protocol and Statistical Analysis Plan

Study Protocol and Statistical Analysis Plan

Background

Engineers from our Small Business partner, Minnesota HealthSolutions, have designed a new prototype child car safety seat. The car seat includes a load leg, which is a relatively new feature that braces the base of the car seat against the floor of the vehicle. The load leg helps to absorb crash forces and prevent movement of the car seat and its occupant during a crash. Load legs already exist on a few car seat models on the market today, but Minnesota Health Solutions has created a new design that absorbs energy in a novel way.

The research team from the Ohio State University (OSU) was involved in a Phase I SBIR with the prototype car seat. In that project, the prototype was shown to 15 volunteer participants (12 caregivers and 3 certified Child Passenger Safety Technicians (CPSTs)). The study participants practiced installing the car seat and gave verbal and written feedback on the understandability and ease-of-use of the load leg. They provided information about their families' travel habits and whether they saw value in the newly designed feature.

In this Phase II SBIR proposal, OSU will conduct additional human subjects testing to gauge the usability of the new car seat safety feature in a more in-depth and quantitative approach.

Objectives

The primary objective is to assess the usability of the load leg design for caregivers who must install the child safety seat into a vehicle. The specific aims are to quantify any errors committed by the participants while installing the car seat and to assess participants' opinions on the car seat's load leg design.

Research design

A descriptive study will be conducted to determine whether human subjects are able to install the new feature of the prototype car seat correctly. Participants will be presented with the prototype car seat and a set of basic written instructions and labels to guide their installations. The percentage of participants who use the new feature and use it correctly will be reported. Any installation errors on other parts of the child seat (seat belt, lower anchors, top tether) will also be reported.

Detailed study procedures

Recruitment

Announcements will be posted in OSU employee newsletters, volunteer mailing lists, department mailing lists, and social media. Interested participants will be asked to email the study team. Study personnel will send a response email to determine if the participant is eligible to participate. Pre-screen questions will identify potential participants who meet the following criteria:

1. Age 18 or older
2. Be a care provider to a child who is up to 2 years of age
3. Have installed a child safety seat in the last 2 years
4. Able to lift and install a child safety seat into a vehicle
5. English-speaking

Participants who meet the above criteria will be asked to schedule an individual appointment.

Enrollment

Participants will be enrolled for one 30 minute time slot. Upon arrival at the scheduled time, participants will be briefed on the study protocol, sign the IRB approved consent form, incentive payment receipt, and will be given the incentive payment.

Session Protocol

Each participant will complete the consent process and sign the consent form. The participant will be asked to install the prototype car seat into a vehicle. A basic set of written instructions and labels on the car seat will be provided. The researcher will explain that they cannot answer any questions during the installation and that the participant may take as long as needed. If a participant completes the installation without using the load leg, this outcome will be noted and then the participant will be prompted to re-install the child seat using the load leg. When each installation is completed, the participant will be led away from the vehicle while a researcher evaluates their work. A researcher who is a CPST will use a data collection form to keep track of all installation errors committed by the participants. The primary outcomes of interest are the rate of load leg installation (without being prompted to use this feature) and correct installation of the load leg. Other errors of interest include routing of the seat belt or lower anchor straps, looseness of attachment, recline angle, etc. A handheld tension gauge will be used to quantify installation tightness. All other metrics are a visual pass/fail metric.

Following the installations, participants will complete a short survey with open-ended queries to describe facilitators or barriers they experienced while installing the seat, as well as what they liked or did not like about the seat. They will use a Likert scale to rate their self-efficacy in installing the seats, if they believed they were installed correctly, and general ease-of-use. Socio-demographic data will also be collected (e.g. gender, age, and socioeconomic status). After study procedures are completed, the researcher will demonstrate how to correctly install the seat and provide the participant with educational materials.

Internal/external validity

Product usability studies are an effective, low-risk way to obtain information about a product design. Published work exists as a model for product usability protocols (for example: Mirman et al. 2015, Mansfield et al. 2018). Product usability studies help to highlight consumer habits and attitudes which engineers and product designers may not be aware of.

Data/statistical analysis

The percentage of participants who install with the load leg (without being prompted) will be recorded. Any installation errors associated with the load leg will also be recorded. Other errors will also be recorded as a percentage of the study sample (belt routing, looseness of attachment, etc.). The rates of these common errors will be compared to those reported in recent literature. There are currently no resources reporting typical error rates for load legs since this feature is not widely available in the current car seat market. The proposed study will provide a benchmark for this factor. Any installation errors with respect to the load leg will be analyzed for their likelihood of causing potential harm to the occupant.

The participant information collected in the surveys will be analyzed using descriptive and inferential statistics. Descriptive statistics such as means, standard deviations, medians, ranges, and frequency distributions will be calculated from the Likert scale data according to type of safety seat. Continuous data will be checked for normality. We will use either paired t-tests or Wilcoxon signed-rank test for correlated data to test the hypothesis of no change on ratings of ease-of-use and self-efficacy. Logistic regression will be used to predict correct load leg usage (pass/fail) using perceived self-efficacy, gender, and age of participants for each device.

Bibliography

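### Nothing in the stated criteria keeps participants naive to the prototype: several caregivers of one child, Phase I volunteers or people told about the seat may enrol, which could inflate the unprompted load leg rate

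*Combined protocol and SAP*

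**What the plan says.** **Who may enrol.** The Recruitment section lists five criteria: adult age, caregiving, recent experience of installing a child seat, physical ability and English. The caregiving criterion reads "Be a care provider to a child who is up to 2 years of age". None of the five concerns household, a relative who has taken part, or earlier exposure to the prototype. They are applied by email: "Pre-screen questions will identify potential participants who meet the following criteria". Recruitment uses open channels: "Announcements will be posted in OSU employee newsletters, volunteer mailing lists, department mailing lists, and social media". Attendance is one person at a time: "Participants who meet the above criteria will be asked to schedule an individual appointment".

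**What participants learn.** Under Session Protocol, a participant who omits the load leg is "prompted to re-install the child seat using the load leg". After the survey, "the researcher will demonstrate how to correctly install the seat and provide the participant with educational materials". The content of those materials is not described.

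**Who has already seen the seat.** The Background reports that 15 Phase I volunteers, 12 of them caregivers, practised installing the prototype and commented on its load leg.

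**What is measured.** Session Protocol states: "The primary outcomes of interest are the rate of load leg installation (without being prompted to use this feature) and correct installation of the load" (the quote stops one word short of the end of the sentence, which names the leg). The Data/statistical analysis section adds: "The percentage of participants who install with the load leg (without being prompted) will be recorded". It plans a simple percentage with no household term, and it presents the study as a benchmark for load leg errors because no comparable figures exist.

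**The concern.** The first primary outcome is meant to show whether a caregiver notices and uses the load leg from the instructions and labels alone. That requires participants who have not heard about it from someone else. The session itself creates informed people, and the criteria let in those closest to them: a second parent, a grandparent or a sitter of the same child, coming to a separate appointment. Phase I caregivers who still meet the criteria, and colleagues on the same mailing lists, are further routes.

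An informed person who fits the leg is counted as an unprompted user. The error runs in one direction, in the product's favour, and a larger sample does not remove it. With no published load leg rate for comparison, an inflated figure would be hard to notice. The survey data named in the protocol (gender, age and socioeconomic status, given as examples) include no household link, so without one the problem could not be corrected afterwards.

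**Working it through.** The documents state no sample size, expected rate or precision target, so there is no figure of the plan's own to reproduce. The inputs below are assumptions, shown over a range.

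**Inputs**
- p: unprompted-use rate in naive participants. Assumed 50%, 70% or 90%.
- q: unprompted-use rate in informed participants. Assumed 95% or 100%.
- f: share of the sample already informed. Assumed 5%, 10% or 20%.

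**Formula.** Expected observed rate = (1 − f) × p + f × q = p + f × (q − p), so bias = f × (q − p).

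Example: p = 50%, q = 95%, f = 10% gives 0.10 × 0.45 = 0.045, so 54.5% is reported in place of 50%.

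**Bias in percentage points**

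| p | q | f = 5% | f = 10% | f = 20% |
|---|---|---|---|---|
| 50% | 95% | 2.25 | 4.5 | 9 |
| 50% | 100% | 2.5 | 5 | 10 |
| 70% | 95% | 1.25 | 2.5 | 5 |
| 70% | 100% | 1.5 | 3 | 6 |
| 90% | 95% | 0.25 | 0.5 | 1 |
| 90% | 100% | 0.5 | 1 | 2 |

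Two reductions apply:
- f counts informed people, not all second household members. If only half of the second members have been told, f halves and so does the bias. For p = 50%, q = 95% and second members at 5%, 10% and 20% of the sample, it is about 1.1, 2.25 and 4.5 points.
- If q lies only halfway between p and 100%, the q = 100% rows halve. For p = 50% they become 1.25, 2.5 and 5 points.

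With f = 0 the bias is zero.

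**Dependence within households.** If a share f are second members of pairs, the design effect is about 1 + 2f × ICC. At f = 5% and an assumed ICC of 0.2 it is 1.02, and the interval widens by √1.02 = 1.01, or 1%. At f = 20% and ICC 0.5 it is 1.20, and the interval widens by √1.20 = 1.095, or about 10%. This effect is minor.

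**Scale against sampling error.** With an assumed n = 50 and p = 50%, the 95% half-width is 1.96 × √(0.5 × 0.5 / 50) = 13.9 points. With n = 100 it is 9.8 points. The bias in the table is below the first figure throughout and just above the second only in the most extreme cell. The half-width shrinks as n grows and the bias does not.

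**The case against.** The strongest case against is that nothing in the documents says the contamination will occur. For the household route, a second caregiver must enrol and the first must have passed on what was learned. A reader might infer that later household members are not naive, but the text supports only that they may not be. That limit stands.

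Other stronger readings also go too far:
- A reader might suppose that participants leave with load leg instructions. The content of the materials is not described, and they may be general child-passenger-safety literature.
- A reader might equate a tip at home with the study's own prompt. That prompt is a researcher's direction after an installation without the leg. All participants also have written instructions and labels, which plausibly mention the leg, so the increment from a tip may be small.
- A reader might conclude that both primary rates are raised. The arithmetic covers unprompted use only. Knowing that the leg exists does not guarantee fitting it correctly, so an effect on correct installation is plausible but not shown.
- A reader might quote a single bias of 2 to 9 points. That holds only for p = 50% and q = 95% with every second member told.

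Two further points stand. A household rule alone would miss Phase I caregivers and colleagues who have heard about the seat. Consent pages were removed from the text available here, so a request for discretion may already exist there.

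The objection leaves the main point intact: as written, the criteria and pre-screen do not check the naivety on which the unprompted-use outcome depends.

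**Conclusion.** The point holds as a gap in eligibility and screening. The stated criteria admit several caregivers of one child, and anyone who already knows the prototype, to a study whose first primary outcome depends on their not having been told about the leg. The resulting bias in the unprompted-use rate would be upward. For 5% to 20% of the sample informed and 95% to 100% use among them, it is about 2 to 10 points at a naive rate of 50%, 1 to 6 at 70% and 0.3 to 2 at 90%, and zero if no one enrolled has been informed. All three inputs are assumptions, and the documents give no basis for choosing among them. The correct-installation rate may also rise, by an amount that cannot be shown.

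The documents do not support saying that the results will be contaminated. This is a descriptive study with no stated decision threshold on its primary rates, so the change is a cheap improvement. It is worth making because the study is offered as a benchmark and the error could not be repaired afterwards without data on household and prior exposure.

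**What to change.** 1. Add a criterion limiting enrolment to one participant per household or child.
2. Add one question to the pre-screen email: has the volunteer, or anyone in the household, taken part in Phase I or Phase II, or seen or been told about the prototype? Exclude those who answer yes. The question should name the prototype seat without mentioning the load leg, so that it does not itself reveal the feature. This also covers Phase I volunteers and informed colleagues, whom a household rule would miss.
3. At debrief, ask participants not to describe the seat to other potential volunteers until the study closes. The safety demonstration and the materials stay as planned.

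If the study team prefers not to exclude, it should record the answer and a household identifier, and report the unprompted-use rate both for all participants and for unexposed first-in-household participants.

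The cost is one criterion, one question, one sentence at debrief and a few volunteers lost.

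### The eligibility criteria neither exclude nor identify child-restraint professionals who are also caregivers, so the usability rates could be biased toward correct use by an unknown amount

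*Combined protocol and SAP*

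**What the plan says.** The Objectives section of the combined protocol and SAP states the primary aim as to "assess the usability of the load leg design for caregivers who must install the child safety seat into a vehicle". The Background describes the Phase I sample as "15 volunteer participants (12 caregivers and 3 certified Child Passenger Safety Technicians (CPSTs", so technicians and caregivers were listed there as two groups.

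For Phase II, Recruitment gives five criteria. Four of them concern adulthood, caring for a child no older than 2, the physical ability to handle and fit a seat, and command of English. The remaining one, third on the list, asks for recent experience: "Have installed a child safety seat in the last 2 years".

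Volunteers who satisfy these go straight to scheduling, and no exclusion criterion is listed. On channels, the plan says: "Announcements will be posted in OSU employee newsletters, volunteer mailing lists, department mailing lists, and social media".

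The Session Protocol mentions a CPST only as the researcher who scores the installations. It names two primary outcomes: unprompted use of the load leg and its correct installation. The survey's socio-demographic items are illustrated by gender, age and socioeconomic status. Under Data/statistical analysis, the logistic regression for correct load leg use has self-efficacy, gender and age as predictors. The same section intends the load leg result as a benchmark, because no typical error rates are available, and plans to compare the other error rates with recent literature.

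**The concern.** A usability rate can be interpreted only if it is clear whose usability was measured. The stated users are caregivers, and the protocol's own account of Phase I treats technicians as a different kind of participant. The Phase II criteria do not carry that distinction forward. A technician or other child-restraint professional with a child up to 2 in their care would be enrolled, scored and counted like any other caregiver.

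The load leg rates are meant as a first benchmark, so later studies may be judged against them. The other error rates will be set beside published ones. If professionals take part and install better, both sets of results would look more favourable than they would for caregivers without that training. Because no planned item records the status, a reader of the results could neither see this nor correct for it. Training could also raise both self-efficacy and correct use, which would complicate the association that the logistic regression is meant to describe.

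**Working it through.** **Step 1: do the criteria admit a professional?** Take a CPST who is an English-speaking adult, cares for a child up to 2, has installed a seat in the last 2 years and is physically able to do so. All five criteria are met and nothing else stands before scheduling. The gap is the missing exclusion. The recent-installation criterion is a minimum-experience rule that ordinary caregivers also meet, and it is not itself at fault.

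**Step 2: could such people be identified afterwards?** The named survey items and the three regression predictors include neither certification nor occupation. The survey items are given as examples, so a further item is possible, but none is planned in the text.

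**Step 3: is there a plan figure to reproduce?** No. The documents state no Phase II sample size, assumed error rate or expected share of professionals. What follows is a sensitivity check on assumed inputs.

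**Step 4: size of a possible bias.** Let f be the share of professionals, e_c the error rate of other caregivers and e_p that of professionals.

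- Reported error rate = (1 − f) × e_c + f × e_p
- Bias = f × (e_p − e_c)

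With e_c = 50% and e_p = 5%, both assumed:

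| f | Reported error rate | Bias (points) |
|---|---|---|
| 1% | 0.99 × 50 + 0.01 × 5 = 49.55% | −0.45 |
| 5% | 0.95 × 50 + 0.05 × 5 = 47.75% | −2.25 |
| 10% | 0.90 × 50 + 0.10 × 5 = 45.5% | −4.5 |
| 20% | 0.80 × 50 + 0.20 × 5 = 41.0% | −9.0 |

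The 20% row is the Phase I share, 3/15, where technicians were a separately listed group. It is an upper illustration and not a forecast.

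**Step 5: vary the gap.** Absolute bias in points, by assumed error rates:

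| e_c, e_p | f = 1% | f = 5% | f = 10% |
|---|---|---|---|
| 50%, 0% | 0.5 | 2.5 | 5.0 |
| 30%, 5% | 0.25 | 1.25 | 2.5 |
| 10%, 5% | 0.05 | 0.25 | 0.5 |

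If professionals do no better, the gap is zero and so is the bias.

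**Step 6: compare with sampling error.** The 95% half-width is 1.96 × √(p(1 − p)/n). At p = 0.50 it is 17.9 points for n = 30, 13.9 for n = 50 and 9.8 for n = 100, with n assumed. A share of 5% or less gives at most 2.5 points in these scenarios, well inside that range. One professional among 30 is a share of 1/30 = 3.3%, which at the 45-point gap is 0.033 × 45 = 1.5 points. Unlike sampling error, this bias does not shrink as n grows if the share stays the same, and the interval does not allow for it.

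**The case against.** The strongest reply is that no bias has been shown. A reader might infer that the rates will be biased because professionals will enrol and will do better. The documents support neither step. They do not say that any professional is expected, and the mailing lists are not tied to any particular department. Nothing suggests that the CPST who scores the sessions, or other study staff, would take part. The load leg design is novel and the feature is not widely available, so the text does not show that professionals would use or install this leg correctly more often. That part of the reply stands and limits the point to a possible bias.

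A second reply is that the objective says caregivers without restricting them to lay people. A technician who is a caregiver then belongs to the stated population, and only over-representation would distort the estimate. The lay restriction is indeed an inference. Phase I's separate count supports it, as does the remark under Internal/external validity that such studies reveal consumer habits unknown to engineers and designers. Naming only caregivers in Phase II can also be read as an intention to leave technicians out. If so, the criteria do not carry that intention through.

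A third reply is that the comparison literature may itself have included professionals, so excluding them might reduce comparability. The documents cannot settle this. The remaining reply, that small shares lie within sampling error, is correct on the figures above. It bears on size and leaves the gap in place.

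**Conclusion.** The point holds as a gap in defining and describing the sample that is cheap to close. The criteria admit CPSTs and other child-restraint professionals who are caregivers, and no named item or covariate would reveal them. If they enrol and perform better, unprompted load leg use, correct installation and the other error rates could all be biased toward correct use.

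The size is unknown. Under the assumed 50% and 5% error rates it is roughly 0.5, 2.3 and 4.5 points at shares of 1%, 5% and 10%, and it falls in proportion if the gap is narrower. These figures rest wholly on assumptions and are not estimates for this study. The expected effect may well be small. The reason to act is that a rate offered as a first benchmark should not carry a possible bias that cannot be detected afterwards when one question would remove it.

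**What to change.** Add one neutral question on certification and occupation to the pre-screen email, worded so that it does not mention the load leg and so does not prompt its use. Use the answer to exclude CPSTs, people who work professionally with child restraints, and members of the study team, and add this to the listed criteria.

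If enrolment has already begun, record the same status for those enrolled and report the primary outcomes and the other error rates with and without them. That split would also help where the comparison literature did not exclude professionals.

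The cost is one extra question, a minor protocol amendment and a few volunteers lost from the pool.

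### Unprompted load leg use is a primary outcome, yet the eligibility criteria admit Phase I volunteers who have already practised with this prototype

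*Combined protocol and SAP*

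**What the plan says.** Session Protocol names two primary outcomes: "The primary outcomes of interest are the rate of load leg installation (without being prompted to use this feature"), and correct installation of the leg. Data/statistical analysis reports the first as a simple percentage of participants, with no adjustment for earlier exposure.

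The outcome is measured with the supplied materials in hand: "A basic set of written instructions and labels on the car seat will be provided". Research design likewise describes "a set of basic written instructions and labels to guide their installations". These materials are part of the product under test.

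The Background reports that Phase I showed the prototype to 15 volunteers (12 caregivers and 3 child passenger safety technicians). They practised fitting it and gave feedback on the load leg. The same university team was involved.

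Recruitment lists five criteria: age 18 or over, caring for a young child ("Be a care provider to a child who is up to 2 years of age"), a seat installation within the last 2 years, physical ability, and English. Eligibility is checked by email ("Study personnel will send a response email to determine if the participant is eligible to participate"), and then "Participants who meet the above criteria will be asked to schedule an individual appointment". Prior participation is not mentioned.

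Under Enrollment, on arrival "participants will be briefed on the study protocol, sign the IRB approved consent form". The content of that briefing is not given.

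**The concern.** A rate of unprompted use describes what people do when they meet the feature through the seat, its labels and its instructions alone. Someone who has already practised with this prototype and been asked for an opinion of its leg no longer meets that condition. Such a person would probably use the leg more often than a newcomer, so the reported percentage would tend to overstate unprompted use. The direction is not certain, because a Phase I volunteer who saw no value in the leg might leave it off.

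The overlap is plausible because both phases involve the same university team and this phase recruits broadly: "Announcements will be posted in OSU employee newsletters, volunteer mailing lists, department mailing lists, and social media". As the plan stands, re-enrolment would not be noticed unless someone asked.

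A lesser question is whether the briefing before installation could reveal the leg or the planned second installation. The plan does not say in so many words that it must not.

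**Working it through.** The plan gives no sample size, expected rate or precision target, so there is no figure of its own to reproduce. The calculation below is an illustration of scale only.

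**Inputs from the documents:** 15 people exposed in Phase I, 12 of them caregivers; no exclusion for them; outcome reported as a raw percentage.

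**Assumed inputs:** sample size N; number of Phase I returners k; their rate of using the leg u; rate among newcomers given the supplied instructions and labels r.

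**Formula.** Observed rate = [(N − k)·r + k·u] / N, so the shift is (k/N)·(u − r).

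**Three returners, r = 50%:**

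| N | k/N | u = 40% | u = 80% | u = 100% |
|---|---|---|---|---|
| 50 | 0.06 | −0.6 points | +1.8 | +3.0 |
| 30 | 0.10 | −1.0 points | +3.0 | +5.0 |

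With k = 0 the shift is zero. If r is higher there is less room to move: at u = 100% and k = 3, the shift at r = 70% is 0.06 × 30 = 1.8 points (N = 50) or 0.10 × 30 = 3.0 points (N = 30).

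**Comparison with sampling error.** The 95% half-width is 1.96·√(r(1 − r)/N). At r = 50% this is 13.9 points for N = 50 and 17.9 points for N = 30. The three-returner shifts lie well inside it.

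**Extreme case.** If all 12 Phase I caregivers returned and all used the leg, the shift at r = 50% would be (12/50) × 50 = 12 points at N = 50 and (12/30) × 50 = 20 points at N = 30. Nothing in the documents suggests that this would happen.

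**Briefing.** If a share q of would-be non-users were cued, the shift would be q·(1 − r): at r = 50%, 5 points for q = 10% and 0 for q = 0. The documents give no basis for any value of q above zero, so this shows sensitivity and is not evidence of bias.

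**The case against.** The strongest reply is that the plan already protects this outcome. Absence of prompting is written into its definition and repeated in the analysis section. Non-use is noted before any prompt is given. Questions are not answered during the installation, and the demonstration comes last. The task as stated is simply to install the prototype seat, and the official title does not name the leg. This answers most of the briefing question. A reader might infer that nothing prevents staff from naming the leg beforehand, or that the briefing does cue participants. Neither is supported: pointing out the leg in advance would contradict the outcome definition on an ordinary reading. The consent, announcement and email wording is not shown in the public file, so nothing can be held against it. What stands is only that no sentence applies the rule expressly to the briefing.

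On Phase I volunteers, the reply is that few could qualify. They, including the three technicians, must now care for a child up to 2 years old and have installed a seat within 2 years. That makes overlap probably small. It does not exclude it, because Phase I dates are not given and a family may have a younger child. It is also fair that prior participation can be established by asking, so this route is not beyond detection. The plan does not list that question, however.

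Finally, the study is descriptive, with no test or threshold attached to this rate. That limits the consequence of a small shift but does not make the rate a measure of naive use.

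**Conclusion.** The point holds as a minor improvement that is cheap to make. As written, the criteria would admit a Phase I volunteer who is not naive to the feature whose spontaneous use is a primary outcome, and the likely effect is to raise the rate. The illustrated size is about −1 to +5 points, assuming three returners, N of 30 to 50, a true rate of 50% and returner use of 40% to 100%; it is zero if none return. N, overlap and all rates are assumptions.

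The documents do not show that any Phase I volunteer will re-enrol, that the briefing names the leg, or that the bias must be upward. No claim is made about correct installation of the leg. The instructions and labels are part of the test condition, and whatever use they produce is not bias.

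**What to change.** 1. Add prior participation in the Phase I prototype study as an exclusion under Recruitment. Ask about it in the existing pre-screen email in general terms, such as previous participation in the team's earlier car seat study, without naming the load leg. The cost is one question and at most 15 people lost from the pool, possibly none.

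2. As a clarification only, add one sentence under Enrollment or Session Protocol. It should say that the pre-installation briefing keeps to the task already stated (install the prototype seat) and does not point out the load leg or the planned re-installation prompt until the first installation is scored. If a briefing script already does this, the protocol need only say so.

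The supplied instructions and labels stay as they are. Neither change adds visits, staff or procedures.

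### Correct load leg installation, a primary outcome, is scored by eye only, so a leg that does not brace on the floor may pass and the benchmark rate may be too favourable

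*Combined protocol and SAP*

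**What the plan says.** All references are to the combined protocol and SAP.

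- **Function of the leg (Background).** The leg "braces the base of the car seat against the floor of the vehicle".
- **Primary outcomes (Session Protocol).** Two are named, and the second concerns whether the leg is fitted correctly: "The primary outcomes of interest are the rate of load leg installation (without being prompted to use this feature) and correct installation of the load" (cut one word short of the sentence's end).
- **Who scores (Session Protocol).** "A researcher who is a CPST will use a data collection form to keep track of all installation errors committed by the participants". A CPST is a certified Child Passenger Safety Technician. The participant is away from the vehicle at that time. The form is not reproduced.
- **How it is scored (Session Protocol).** "A handheld tension gauge will be used to quantify installation tightness". The next sentence covers everything else: "All other metrics are a visual pass/fail metric".
- **Use of the result (Data/statistical analysis).** No error rates for load legs are available elsewhere, and "The proposed study will provide a benchmark for this factor". Load leg errors are also to be judged for how likely they are to harm the child, and the pass/fail result is modelled: "Logistic regression will be used to predict correct load leg usage (pass/fail) using perceived self-efficacy, gender, and age of participants for each device".

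The plan does not define a correctly installed load leg, does not say how floor contact is verified, and describes no physical check of the leg.

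**The concern.** Looseness of attachment, which the Session Protocol lists among the other errors, gets a physical measurement. Correct load leg installation, a primary outcome, gets a look. Yet the leg's stated purpose is mechanical: it has to brace the base against the floor. A gap under the foot can in principle be seen. Contact that carries nothing, or an adjustment step left incomplete, may not be.

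If such legs are passed, three results are affected:

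- **The benchmark.** The correct-installation rate is too high, and the plan itself says there is no outside rate that would expose this.
- **The harm assessment.** An error that is not recorded never enters it, although a leg that does not brace is the failure closest to the leg's purpose.
- **The logistic regression.** Its outcome is the same pass/fail result, so any misclassification carries over.

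None of this can be repaired in the analysis, because the plan provides for no record of the leg's physical state.

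**Working it through.** The plan states no sample size, expected rate or rater accuracy, so there is no figure to reproduce. The check has two parts.

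**1. Does the visual rule cover the load leg?**
The Session Protocol names one instrumented quantity, installation tightness, and does not link it to the leg. The next sentence makes all other metrics visual. Correct leg installation is one of those. The rule governs how items are scored, so a floor-contact item on the unseen form would also be scored by eye.

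**2. How large could the effect be?**
Inputs, all assumptions:

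- p = true proportion of legs installed correctly
- s = share of incorrect legs that pass a visual check
- f = share of correct legs that fail a visual check

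Reported rate = p × (1 − f) + (1 − p) × s

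With f = 0 this becomes p + (1 − p) × s, so the excess is (1 − p) × s.

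| True p | s = 0 | s = 0.1 | s = 0.25 | s = 0.5 |
|---|---|---|---|---|
| 0.50 | 0.50 | 0.55 | 0.625 | 0.75 |
| 0.70 | 0.70 | 0.73 | 0.775 | 0.85 |
| 0.80 | 0.80 | 0.82 | 0.85 | 0.90 |
| 0.90 | 0.90 | 0.91 | 0.925 | 0.95 |

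At p = 0.80 the excess is 0.20 × 0.1 = 0.02 up to 0.20 × 0.5 = 0.10. Seen from the error side, the reported failure rate is (1 − p) × (1 − s). It therefore falls short of the true failure rate by the fraction s, whatever p is.

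**Sensitivity to false fails.** If sight also fails some correct legs, the sign can turn. At p = 0.80, s = 0.25 and f = 0.10, the reported rate is 0.80 × 0.90 + 0.20 × 0.25 = 0.72 + 0.05 = 0.77, which is 3 points too low. The two errors cancel when f = (1 − p) × s / p = 0.20 × 0.25 / 0.80 = 0.0625.

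**The case against.** The strongest reply is that the documents do not show the visual check to be inadequate.

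- **Inspection may be good enough.** A trained technician looks at every installation, and a foot hovering above the floor is a visible gap. If the prototype has a visible contact or lock indicator, s could be close to zero. This stands. The effect is possible, not shown.
- **The unseen form may contain a contact item.** It may, but under the stated rule that item would be scored visually. If the team in fact checks by hand, the sentence is inaccurate and needs correcting anyway.
- **Bracing is described for a crash, not for installation.** The Background does not say that the foot must be under load, or resist sliding or lifting, once installed. It describes no length lock either. This stands. A pass rule built on sliding or lifting the foot would be the reviewer's own invention and could fail legs installed as instructed. The prototype's instructions have to define correctness.
- **The direction is not certain.** A fault that cannot be seen can only be missed, so this mechanism only raises the rate. False fails would work the other way. The documents suggest no mechanism for them, but they do not exclude them.
- **A hand check could disturb the seat.** Handling the leg before the tension reading might change the study's one instrumented measure. This is a fair point, and the order of steps in the fix answers it.

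A reader might go further and infer that non-bearing legs will be counted as correct and that the benchmark is biased upward. The documents do not support that. No section says such legs are passed, how often they occur, or how well sight detects them.

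**Conclusion.** The point holds in a limited form. By the plan's own rule, a primary outcome is scored by eye only, although the leg's stated function is to brace against the floor. Legs that are not secured as the instructions require may therefore be passed, and the benchmark rate may be too favourable.

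The size depends wholly on s, for which the documents offer nothing. The range of 0.1 to 0.5 is illustrative, and the upward direction assumes that false passes outweigh false fails. The rate of unprompted use is unaffected, because it depends on whether the leg was used and not on how well.

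This is an improvement the sponsor should make, held with medium confidence. It is not a flaw that invalidates the study.

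**What to change.** Replace the blanket visual rule for the load leg with a sequence carried out by the same technician at the same evaluation:

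1. Record the visual pass/fail verdict on the leg.
2. Take the tension gauge reading.
3. Make a brief hands-on check of floor contact, and of any adjustment or locking step that the prototype's own instructions contain. Record each as yes or no.

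Define a correct leg in the protocol from those instructions, not from a new slide or lift test. Make the hands-on check on every leg used, whatever the visual verdict, so that disagreement in either direction is on record.

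Report two rates: correct by visual verdict alone, and correct by visual verdict plus hands-on check. The first keeps the planned measure. The difference shows how many visual passes the hands-on check overturns. If there is none, the study has evidence that the visual score was sufficient. State which rate is the benchmark and which is the regression outcome, and include errors found by hand in the harm assessment.

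**Cost.** A few tick boxes and a little time per installation, with no extra staff or equipment. The reported correct rate may come out slightly lower.
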